CSSRS	Columbia Suicide Severity Rating Scale
Red	
CV	coefficient of variation
DEC	Dose Escalation Committee
ECG	electrocardiogram
eCRF	electronic case report form
Redact	
GFR	glomerular filtration rate
GIP	gastric inhibitory peptide
GLP-1	glucagon-like peptide-1
HbA1c	hemoglobin A1c (glycated hemoglobin)
HDL	high-density lipoprotein
Hg	mercury
HR	Heart rate
ITT	intent-to-treat
IV	intravenous(ly)
IXRS	interactive voice or web response system
LDL	low-density lipoprotein
MAD	multiple-ascending dose
MedDRA	Medical Dictionary for Regulatory Activities
MMT	mixed-meal test
NASH	non-alcoholic steatohepatitis
NOAEL	no-observed-adverse-effect level
PD	pharmacodynamic(s)
PK	pharmacokinetic(s)
Reda	
PR(PQ)	ECG interval measured from the onset of the P wave to the onset of the QRS complex
QRS	ECG interval measured from the onset of the QRS complex to the J point
QT	ECG interval measured from the onset of the QRS complex to the offset of the T wave

Abbreviation or Specialized Term	Definition
QTc	cardiac QT interval corrected for heart rate
QTcF	cardiac QTc interval corrected for heart rate by the formula of Fridericia
RR	The time between corresponding points on 2 consecutive R waves on the ECG
SAE	serious adverse event
SID	subject identification
SC	subcutaneous(ly)
T2DM	type 2 diabetes mellitus
TG	triglycerides
T _{max}	time to maximum observed concentration
ULN	upper limit of normal
w/v	weight per volume

1 INTRODUCTION

This document describes the statistical analysis for protocol D5670C00002, an investigation of MEDI0382 in overweight and obese subjects with a history of Type 2 Diabetes Mellitus.

Redacted

This study is designed to assess the efficacy, safety/tolerability, and PK of MEDI0382 and pharmacodynamics (PD) effect on blood glucose, following SC administration of multi-ascending doses. This document details the statistical analyses that will be performed and describes the general conventions and definitions that will be used.

In addition, a set of table templates and specifications is planned to be created in a statistical programming plan (SPP) to complement this document.

2 STUDY OVERVIEW

2.1 Study Objectives

2.1.1 Primary Study Objective(s)

The primary objective of this study is to assess the effect of MEDI0382 on glucose control (as measured by the standardized MMT glucose data) and body weight from baseline to the end of a 4-week period at a stable dose.

2.1.2 Secondary Study Objectives

1. To assess the effect of MEDI0382 on glucose control as measured by the standardized MMT, HbA1c, and fructosamine data from baseline through end of treatment
2. To characterize the safety profile of MEDI0382 following SC administration of multiple-ascending doses
3. To characterize the PK and immunogenicity of MEDI0382
4. To characterize the PD effect of MEDI0382 on glucose metabolism following a MMT

2.1.3 Exploratory Study Objectives

Redacted

Redacted

[Redacted]

[Redacted]

5. To explore the effect of MEDI0382 on the volume and fat/water content of the liver
6. To explore the effect of MEDI0382 on visceral and subcutaneous fat

2.2 Study Design

This is a randomized, double-blind, placebo-controlled study in 2 parts (A and B) with approximately 75 overweight or obese subjects with relatively well controlled T2DM (without significant late diabetic complications) planned for enrollment across up to 10 study sites.

Part A is designed to establish a dose titration regimen for MEDI0382 and a maximal effective dose after titration in T2DM subjects maintained on metformin therapy and Part B is designed to establish the efficacy of MEDI0382 on weight and glycemic control.

Redacted

[Redacted]

[Redacted]

[Redacted]

[Redacted]

[Redacted]

[Redacted]

[Redacted]

The study design schematic is presented in Figure 2.2-1. More details on the study design can be found in section 3.1 in the protocol.

Part A:
Cohorts 1 through 3

Key endpoints:
Safety/tolerability and PK

Cohort 3: (6 MEDI0382 + 3 placebo)

Initial dose 4 days	Titration dose 1 4 days	Titration dose 2 7 days
------------------------	----------------------------	----------------------------

Cohort 2: (6 MEDI0382 + 3 placebo)

Initial dose 4 days	Titration dose 1 7 days
------------------------	----------------------------

Cohort 1: (6 MEDI0382 + 3 placebo)

Stable dose 7 days

Part B:
Cohort 4

Key endpoints:
Body weight, glycemic control, safety/tolerability

24 MEDI0382 + 24 placebo

[figure not shown]

Figure 2.2-1 Study Flow Diagram

2.3 Treatment Assignment and Blinding

Subjects will receive MEDI0382 or placebo. Subject assignment within a cohort is blinded. For Cohorts 1, 2, and 3, nine subjects in each cohort will be randomized in a 2:1 ratio to receive MEDI0382 or placebo. For Cohort 4, a total of 48 subjects will be randomized in a 1:1 ratio to receive MEDI0382 or placebo. The IXRS will assign a unique randomization code and treatment arm for the subject.

MEDI0382 and placebo are identically labeled and indistinguishable in appearance. As such, the pharmacist, the subject/legal representative, the investigator/ staff who are involved in the treatment or clinical evaluation of the subjects, and the CRO personnel responsible for managing and monitoring the study will NOT be aware of the treatment received. Medimmune will not be blinded to treatment allocation to allow for evaluation of data for

dose escalation decisions (including safety, and PK data) and for SAEs that are unexpected and are suspected to be causally related to an investigational product, and that potentially require expedited reporting to regulatory authorities.

2.4 Sample Size

The sample size of 6 subjects in the MEDI0382 group and 3 subjects in the placebo group for Cohorts 1, 2, and 3 was empirically determined to obtain adequate safety and tolerability evaluation. Under a two-sided 10% significance level, a sample size of 44 evaluable subjects (22 per arm) for Cohort 4 will provide 80% power to detect weight loss of 1.5 kg versus placebo (assuming a standard deviation of 1.9 kg), and 98% power to detect a 20% relative reduction in MMT glucose AUC (up to 240 minutes post-MMT) versus placebo at the end of treatment (assuming a coefficient of variation [CV] of 17%). (Internal data from another investigational agent for T2DM showed a CV of 17% for 24-hour glucose AUC, and the CV for glucose AUC [up to 240 minutes post-MMT] is expected to be similar.) The sample size for Cohort 4 is adjusted to 48 subjects (24 per arm) to account for a 10% drop-out rate. For Cohorts 5 and 6, under a one-sided 2.5% significance level the combination of 24 subjects in the MEDI0382 and 8 subjects in placebo from both cohorts will provide 80% power to rule out more than 20% of MEDI0382 subjects having > 5 mm Hg increase from baseline in diastolic BP on the seventh day of the 300 µg dose level (Day 22 visit of Cohort 5 and Day 17 visit of Cohort 6) relative to that of placebo subjects under the assumption that both placebo and MEDI0382 subjects have a true rate of 1% with > 5 mm Hg increase from baseline in diastolic BP. Moreover, under a one-sided 2.5% significance level, this sample size will provide 88% power to rule out > 20 bpm pulse rate increase from baseline on the seventh day of the 300 µg dose level in MEDI0382 subjects relative to that of placebo subjects with assumed standard deviation of 15 bpm.

3 STATISTICAL METHODS

3.1 General Considerations

Data will be provided in data listings sorted by treatment group and subject number. Tabular summaries will be presented by treatment group. Categorical data will be summarized by the number and percentage of subjects in each category. Continuous variables will be summarized by descriptive statistics, including mean, standard deviation, median, minimum, and maximum. Baseline values will be defined as the measurements at Day 1 pre-dose unless data are not available; in which case, baseline value will be the last assessment prior to the first administration of investigational product. Data analyses will be conducted using the SAS® System Version 9.3 or higher (SAS Institute Inc., Cary, NC).

3.2 Analysis Populations

The analysis populations are defined in Table 3.2-1.

Table 3.2-1 Analysis Populations

Population	Description
Intent-to-treat (ITT) population	The intent-to-treat (ITT) population includes all subjects who are randomized and receive any investigational product analyzed according to the initial randomization.
As-treated population	The As-treated population includes all subjects who receive any investigational product analyzed according to the treatment they actually receive.
PD population	The PD Population includes all subjects who received at least 1 dose of investigational product and participated in at least 1 MMT (ie, gave at least 1 post-MMT PD blood sample).
PK population	The PK Population includes all subjects who received at least 1 dose of investigational product and had at least one PK sample taken that is above the lower limit of quantitation.

3.3 Study Subjects

3.3.1 Subject Disposition and Completion Status

The summary of subject status at the end of the study will include the number and percentage of subjects who completed the study and the number and percentage of subjects who did not complete the study due to reasons such as: lost to follow up, withdrawal of consent, death, or other. This summary will be presented by treatment group and for all subjects combined. The placebo subjects for the summary will be pooled from all Cohorts.

3.3.2 Demographics and Baseline Characteristics

Demographic information and baseline characteristics will be summarized by treatment group and for all subjects combined. The placebo subjects for the summary will be pooled from all Cohorts. Demographic information will include: gender, age (years), ethnicity, race, weight (kg), height (cm), and body mass index (BMI) (kg/m²). A summary of baseline

characteristics may include but not limited to eGFR, baseline medication use, HbA1c, glucose, insulin, blood pressure, and pulse rate etc.

$BMI = \text{weight (kg)} / [\text{height (m)}]^2$

eGFR will be using the MDRD formula (Levy et al 2006).

$eGFR = 175 \times \text{standardized Serum Creatinine}^{-1.154} \times \text{age}^{-0.203} \times 1.212 [\text{if black}] \times 0.742 [\text{if female}]$

All summaries of continuous characteristics will be based on non-missing observations. For categorical characteristics, percentage will be calculated, and the denominator for each percentage is the number of subjects with non-missing data for that particular demographic or baseline parameter.

No statistical test will be performed for comparison of any baseline measurement among treatment groups.

3.3.3 Study Drug Exposure

The number of study drug (investigational product) doses received will be summarized. In addition, the number and percentage of subjects who received all scheduled doses and reasons for full dose not received will be summarized by treatment group.

3.3.4 Concomitant Medications

Concomitant medications will be coded using current AstraZeneca Drug Dictionary (AZDD). Concomitant medications will be summarized using frequency count and percentage by the highest anatomical therapeutic chemical (ATC) class and preferred term. All concomitant medications will be presented in a data listing.

3.4 Efficacy Analyses

3.4.1 Primary Efficacy Endpoints and Analyses

3.4.1.1 Primary Efficacy Endpoints (Cohort 4 only)

1. Percent change from baseline in MMT glucose AUC (up to 240 minutes post-MMT) to end of treatment
2. Change from baseline in body weight in kg to end of treatment

3.4.1.2 Handling of Dropouts and Missing Data

Last observation carry forward (LOCF) will be applied for missing data for efficacy endpoints, that is, a missing measurement at the end of treatment will be replaced with the last available post-baseline measurement.

3.4.1.3 Primary Efficacy Analyses

The percent change in MMT glucose AUC (up to 240 minutes post-MMT) and change in weight from baseline (Day 1) to the end of treatment in Cohort 4 will be compared between MEDI0382 and placebo groups using an analysis of covariance by adjusting for baseline measurement and treatment group. The comparison will be conducted at a two-sided significance level of 0.1. The ITT Population in Cohort 4 will be used for the analyses.

3.4.2 Secondary Efficacy Endpoints and Analyses

3.4.2.1 Secondary Efficacy Endpoints

Change from baseline in HbA1c and fructosamine, and percent change from baseline (Day -1) in 24-hour glucose AUC post-MMT through end of treatment in Cohort 4, and percent change in MMT glucose AUC (up to 240 minutes post-MMT), and change in weight from baseline through end of treatment in all cohorts will be analyzed similarly to the primary efficacy endpoints.

3.4.2.2 Secondary Efficacy Analyses

Change from baseline (Day -2) in HbA1c and fructosamine, and percent change from baseline (Day -1) in 24-hour glucose AUC post-MMT will be analyzed similarly to the primary efficacy endpoints based on ITT population. The 24-hour glucose AUC analyses will include glucose measures from the pre-/post-MMT glucose metabolism panel as well as serum chemistry glucose levels and PD glucose samples, where those results are from unique time points.

3.4.3 Exploratory Efficacy Endpoints and Analyses

3.4.3.1 Exploratory Efficacy Endpoints

- Redacted [REDACTED]
- [REDACTED]
- [REDACTED]
- [REDACTED]
- [REDACTED]

- Lipid endpoints: fasting high-density lipoprotein, low-density lipoprotein, triglycerides, non-esterified fatty acids, and beta-hydroxybutyrate
- **Redacted** [Redacted]
[Redacted]
 - [Redacted]
[Redacted]
 - [Redacted]
 - [Redacted]

3.4.3.2 Exploratory Efficacy Analyses

Redacted [Redacted]
[Redacted]
[Redacted]
[Redacted]
[Redacted]

[Redacted]
[Redacted]
[Redacted]
[Redacted]

[Redacted]
[Redacted]
[Redacted]
[Redacted]
[Redacted]
[Redacted]

[Redacted] Lipid endpoints (fasting high-density lipoprotein (HDL), low-density lipoprotein (LDL), triglycerides (TG), non-esterified fatty acids, and beta-hydroxybutyrate)), and liver function endpoints as determined by MRI (Cohort 4 only) will be measured at the specified time points. They will be descriptively summarized by treatment group at specified time points. In addition, the change in those parameters from baseline to the end of treatment will be compared between MEDI0382 and placebo groups using an analysis of covariance by adjusting for baseline measurement and treatment group.

Redacted

ITT population will be applied for those analyses.

3.5 Pharmacodynamics Endpoint(s) and Analyses

3.5.1.1 Pharmacodynamics Endpoint(s)

PD endpoints (glucose metabolism panel):

- a. Glucose
- b. Beta cell health: insulin, pro-insulin, and c-peptide
- c. Incretins: GLP-1 (active and inactive), glucagon, gastric inhibitory peptide (GIP)

3.5.1.2 Analysis of Pharmacodynamics Endpoint(s)

PD endpoints will be descriptively summarized by treatment group at the specified time points. The summary will be provided for each cohort separately due to different MEDI0382 dose levels and/or different collection schedules across cohorts. Change in fasting measurement from baseline (Day -1) and percent change in 4-hour AUC from baseline of the PD endpoints to the end of treatment will be compared between MEDI0382 and placebo groups using an analysis of covariance by adjusting for baseline measurement and treatment group based on ITT population.

Beta cell function will be derived using the Homeostasis Model Assessment (HOMA) calculation from fasting glucose and insulin data, and insulin sensitivity will be derived from MMT data using the HOMA-2 IR algorithm and the modified Matsuda index calculation. Change from baseline (Day -1) to the end of treatment will be compared between MEDI0382 and placebo groups using an analysis of covariance by adjusting for baseline measurement and treatment group based on ITT population.

Change from baseline of glucose measured by glucometer on each measurement day will be descriptively summarized by daily average due to high variability nature of the glucose values. Change from baseline to the end of treatment will be compared between MEDI0382 and placebo groups using an analysis of covariance by adjusting for baseline measurement and treatment group based on ITT population.

3.6 Safety Analyses

The analyses will be based on the As-treated population. All safety summaries will be presented by treatment group for each cohort. Since the treatment schedule and follow up duration is different across cohorts, the placebo subjects will not be pooled across cohorts.

3.6.1 Adverse Events and Serious Adverse Events

Analysis of safety will include the type, incidence, severity and relationship to study investigational product summarized by MedDRA system organ class and preferred term by treatment group for each cohort. Specific AEs will be counted once for each subject for calculating percentages. In addition, if the same AE occurs multiple times within a particular subject, the highest severity and level of relationship observed will be reported. Non-treatment-emergent AEs/serious adverse events (SAEs) will be presented in the listings.

3.6.2 Adverse Events of Special Interest

The following AESIs have been identified specifically for this protocol and are to be reported as described in the Sections of Recording of Adverse Events and Reporting of Serious Adverse Events in the protocol:

1. Any arrhythmia deemed by the investigator to be clinically significant.
2. Any vomiting (vomiting is known to be associated with GLP-1 receptor agonist use) Hepatic function abnormality meeting the definition of Hy's law is considered an AESI. See the Section of Hepatic Function Abnormality in the protocol for the definition and reporting of AESIs of hepatic function abnormality.

The AESIs will be summarized overall, as well as categorized by MedDRA system organ class and preferred term by treatment group for each cohort.

3.6.3 Deaths and Treatment Discontinuations due to Adverse Events

Death and AEs resulting in discontinuation from the study drug permanently will be summarized. The summary includes overall, categorized by MedDRA system organ class, and preferred term.

3.6.4 Clinical Laboratory Evaluation

Hematology, serum chemistry, and urinalysis laboratory evaluations will be conducted during the study. The hematology and serum chemistry parameters as well as their changes from baseline will be summarized with descriptive statistics (number of subjects, mean, and standard deviation, median, minimum and maximum) by treatment group at each of the time points specified in Treatment and Follow-up Period Study Procedures in the protocol. The

hematology and serum chemistry results will also be classified into low, normal, and high. The urinalysis results will be classified into normal and abnormal. The shift from baseline hematology, serum chemistry, and urinalysis results will be summarized by treatment group at each of specified time points. The criteria for each parameter will be provided in statistical programming plan (SPP).

3.6.5 Other Safety Evaluation

3.6.5.1 Vital Signs

Vital signs including pulse rate (bpm), blood pressure (mm Hg), temperature (°C), weight (kg), and respiratory rate (/min), as well as the change from baseline for each of those parameters will be descriptively summarized by treatment group at each of the specified time points in the protocol.

Pulse and BP during the at-home self-administration period for Cohorts 4, 5, and 6, as measured by the ABPM, will be summarized and listed separately from vital signs data. Pulse and diastolic BP in Cohorts 5 and 6 will be compared between MEDI0382 and placebo groups using an analysis of covariance by adjusting for baseline measurement. In addition, a one-sided 2.5% upper confidence interval will be provided for the difference between MEDI5884 and placebo groups in percentages of subjects with > 5 mmHg increase from baseline in diastolic BP on seventh day of the 300 mcg dose level for Cohorts 5 and 6 combined.

3.6.5.2 Electrocardiogram

Electrocardiogram parameters will be assessed using telemetry and standard 12-lead electrocardiography. The following ECG parameters as well as the change from baseline for each of those parameters will be reported and descriptively summarized by treatment group at each of the specified time points for Part A and Part B in the protocol: Heart rate, RR, PR, QRS and QT intervals as well as derived parameters QT corrected interval QTcF (Fridericia's formula $\frac{QT}{\sqrt[3]{RR}}$).

3.6.5.3 Columbia-Suicide Severity Rating Scale (C-SSRS) score

Due to small sample size and short follow up duration, suicide-related events are expected to be rare. A listing and a table (if data is warranted) will be provided as following. No formal statistical hypothesis testing will be performed. As-treated population will be used for the analyses.

3.7 Immunogenicity

Immunogenicity of MEDI0382 will be assessed on the time points specified in the tables of Schedule of Treatment Period Procedures and early discontinuation. The number and percentage of subjects in each treatment group showing an immunological response to MEDI0382 will be summarized by study visit, for As-Treated population and by cohort. In the summary, all post-dose immunogenicity results will also be summarized under “Any Visit” category. A subject will be counted as having detectable antibodies at “Any Visit”, if the subject has detectable antibodies at any post-dose visit. The subject will be counted as not having detectable antibodies at “Any Visit” if all post-dose immunogenicity assessments have no MEDI0382 antibody. The subject will be counted as having a missing result at “Any Visit” if all post-dose results for the given test for the subject are missing or if the subject has at least one missing post-dose result for the given test and the remaining results are normal.

For those with a positive post-baseline assessment the percentage who was persistent positive and transient positive will also be presented.

Persistent positive is defined as positive at ≥ 2 post-baseline assessments or positive at last post-baseline assessment.

Transient positive is defined as negative at last post-baseline assessment and positive at only one post-baseline assessment.

All valid assay results from subjects who receive any investigational product will be included in immunogenicity summaries. Study discontinuation blood samples will be summarized at the closest nominal time point that does not already have a value. All assay results along with their titer information and cross reactivity to GLP-1 and glucagon will be listed will be shown in a by-subject listing.

If warranted by the data, the association of ADA positivity with observed PK data and safety may be explored.

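### The antibody summary in SAP Section 3.7 ignores baseline status, and its Any Visit rule treats incomplete positives and incomplete negatives differently without stating a denominator

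*SAP*

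**What the plan says.** SAP Section 3.7 introduces the table as follows: "The number and percentage of subjects in each treatment group showing an immunological response to MEDI0382 will be summarized by study visit". It is presented for the As-Treated population and by cohort, with an added Any Visit category that has three outcomes:

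- Positive: "if the subject has detectable antibodies at any post-dose visit".
- Negative: "if all post-dose immunogenicity assessments have no MEDI0382 antibody".
- Missing: when every post-dose result is missing, or "if the subject has at least one missing post-dose result for the given test and the remaining results are normal".

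Positive subjects are then split in two: "Persistent positive is defined as positive at ≥ 2 post-baseline assessments or positive at last post-baseline assessment", and "Transient positive is defined as negative at last post-baseline assessment and positive at only one post-baseline assessment". Neither definition refers to the baseline result. The section has no treatment-emergent category, and it does not say whether subjects classed as missing stay in the percentage denominator. It also states: "All valid assay results from subjects who receive any investigational product will be included in immunogenicity summaries". Assay results, with titres, go into a by-subject listing.

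**The concern.** Two separate features matter.

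The first is baseline status. The table is introduced as showing a response to the drug, but the classification uses post-dose results alone. Antibody that was present before the first dose and remains detectable is counted with antibody that the drug induced, and the persistent/transient split inherits the mixture.

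The second is asymmetry. One positive sample settles a subject's status however many samples are missing, while a negative needs a complete set. Incomplete positives are kept and incomplete negatives are set aside. What this does to the percentages depends on a denominator that the section leaves open.

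Characterising immunogenicity is part of the third secondary objective (Section 2.1.2). Section 3.7 also allows antibody positivity to be explored against PK and safety, so a misclassified subject would carry into that work.

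**Working it through.** The SAP gives no antibody rate, so there is no figure to reproduce. The rules can be followed through and their effect sized under stated assumptions.

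**Inputs from the SAP.** Cohorts 1-3 have 6 active and 3 placebo subjects each, and Cohort 4 has 24 per arm (Sections 2.3 and 2.4). The only explicit denominator rule, non-missing data, is in Section 3.3.2 and covers demographic and baseline parameters only.

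**Assumed inputs (not in the SAP).** Baseline-positive share that stays positive post-dose, b: 0-10%. Incidence among baseline-negatives, t: 20%. Share of negatives with at least one missing sample, u: 10-20%. Alternatively, 3-5 post-dose samples with 5-10% missing per sample, completely at random.

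**1. Baseline status.** Reported rate = b + (1 − b)t.

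- b = 0: 20%, no distortion.
- b = 5%: 0.05 + 0.95 × 0.20 = 24%.
- b = 10%: 0.10 + 0.90 × 0.20 = 28%.

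In counts, one pre-existing positive adds 1/6 = 16.7 points in an active arm of Cohorts 1-3, or 1/24 = 4.2 points in Cohort 4.

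**2. Asymmetry, with missing subjects excluded from the denominator.** Let π be the true share ever positive, with all positives retained. Reported rate = π / [1 − u(1 − π)]. With π = 20%:

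- u = 10%: 0.20 / (1 − 0.08) = 0.20/0.92 = 21.7%.
- u = 20%: 0.20 / (1 − 0.16) = 0.20/0.84 = 23.8%.

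A per-sample version allows a true positive to be missed too. Let q be the chance that at least one positive sample is observed and c the chance that a true negative has every sample. Reported rate = πq / [πq + (1 − π)c]. For example, take 3 samples, 5% missing and one positive sample: q = 0.95, c = 0.95³ = 0.857, and the rate is 0.190 / (0.190 + 0.686) = 21.7%. Over 5-10% missing per sample the range is 21.7-25.3% with 3 samples and 23.5-29.7% with 5. Since q is at least c, this rate never falls below π.

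**3. Asymmetry, with all As-Treated subjects in the denominator.** The positive rate is πq, which is 18.0-20.0% over the same settings, so there is no inflation. The negative rate suffers instead: with u = 10-20%, a true 80% is shown as 0.80 × 0.90 = 72% down to 0.80 × 0.80 = 64%, and the rest appears as missing.

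**4. Count illustration, Cohort 4 active arm.** With 4 positive and 4 classed as missing, the rate is 4/24 = 16.7% or 4/20 = 20.0%, depending only on the unstated denominator.

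**The case against.** The strongest reply is that the Any Visit row counts subjects with detectable antibodies and is labelled so; the SAP never calls it treatment-emergent incidence. Each cohort has a concurrent placebo group that shows background reactivity, and the titre listing lets a reader separate pre-existing from induced antibody. This mitigates the problem but does not remove it: the table is introduced as showing response to the drug, and neither placebo nor a listing corrects the tabulated active-arm figure.

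On the missing rule, it is cautious not to call a subject negative when an unobserved sample might have been positive. That stands. The difficulty is that the caution is applied to negatives only, and the denominator is left unstated.

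Three stronger readings are tempting and should not be adopted.

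- A reader might infer that the missing rule contradicts the sentence "All valid assay results from subjects who receive any investigational product will be included in immunogenicity summaries". It does not. A valid negative result still enters the by-visit rows; Any Visit is an additional subject-level classification in which missing is a defined outcome.
- A reader might infer that the missing rule inflates the positive rate outright. It does so only if missing subjects leave the denominator. Section 3.7 does not say that they do, and the rule in Section 3.3.2 does not reach this table.
- A reader might infer that early discontinuers are selectively lost as negatives. Section 3.7 does not say whether visits after withdrawal count as missing results, and it lets a discontinuation sample fill one open time point. That sample may not cover several missed visits, so the concern is possible but not shown.

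The sizes rest on assumptions. The simple 2-4 point shift from missing samples is less than one subject in an arm of 24.

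**Conclusion.** The point holds in two parts. First, Section 3.7 classifies antibody status from post-dose results only, so pre-existing antibody that remains detectable is counted as a response and can be labelled persistent. The size depends on a baseline prevalence that the SAP does not give: zero if no subject is positive at baseline, but a visible jump per subject in cohorts with 6 active subjects.

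Second, the Any Visit rule is asymmetric and its denominator is unstated. One choice biases the positive percentage upward and the other understates the negative percentage. The direction follows from the rule; the amounts rest on the assumed 20% rate and the assumed sampling losses.

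The antibody summary is descriptive, with no test attached. This is a modest-priority amendment that makes the reporting of a secondary objective clearer and less biased.

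**What to change.** Amend Section 3.7 as follows.

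- Tabulate baseline-positive subjects separately. Define treatment-emergent antibody as negative at baseline and positive post-dose, or a titre rise of a size fixed in advance in a subject positive at baseline.
- Apply the persistent and transient definitions to treatment-emergent cases only.
- State the Any Visit denominator as subjects with at least one valid post-dose result. Count a subject negative if all available post-dose results are negative.
- Show the number of subjects with incomplete sampling beside the percentages.

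The cost is SAP wording and about one extra table row, from assay and titre data already planned. It needs a baseline antibody sample, which the SAP's post-baseline wording implies and the protocol schedule should confirm.

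The downside is small: a subject positive only at a missed sample is counted negative. In the per-sample illustration, a true 20% is then reported as 18.0-20.0%, against 21.7-29.7% if the current rule is used with missing subjects excluded. The count of incompletely sampled subjects lets the reader judge this.
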